All Delayed Serious Adverse Events (occurring after this 30-day period) considered reasonably related to the protocol treatment(s) or research should be reported without time limitation.

The declaration is made by sending by fax the "notification of a serious adverse event" form (cf. appendix 10) documented as precisely as possible, dated and signed, within 24 working hours following their observation to: [name]

The investigator will note for each event, among other things:

- Its description as clearly as possible according to medical terminology,
- Intensity,
- The start and end date of the event,
- The measures undertaken and whether or not corrective treatment is necessary,
- If the trial treatment was discontinued,
- Its evolution. In the case of a non-fatal event, the evolution will have to be followed until the recovery or the return to the previous state or the stabilization of possible after-effects,
- The causal relationship between this event and the treatment being tested or a constraint related to the research (period without treatment, additional examinations requested as part of the research, etc.),
- The causal relationship with the condition treated, another condition or another treatment. The investigator must also attach to the serious adverse event report, whenever possible:
 - A copy of the hospitalization or extension of hospitalization report,
 - A copy of the autopsy report if required,
 - A copy of all results of additional tests performed, including relevant negative results, with the normal laboratory values attached,
 - Any other document that it deems useful and relevant.

All these documents must be anonymized.

Additional information may be requested (by fax, telephone or during a visit) by the monitor and/or the promoter.

b. Responsibility of the promoter

Upon receipt of the investigator's report of the serious adverse event, the sponsor should issue an opinion on the causal relationship between the serious adverse event and the study product(s).

If the serious adverse event is related by the investigator and/or sponsor to one of the study products (i.e., it is a serious adverse event), the investigator and/or sponsor must establish the expected or unexpected nature of the event.

If it is a serious unexpected adverse reaction, or if it is a new fact, the sponsor writes an initial report which will be transmitted to the ANSM, the CPP and the EMA (via EudraVigilance) within 7 days in case of death, otherwise within 15 days.

If it is an expected serious adverse event, it will be collected for the semi-annual and annual safety reports.

4. Modalities and duration of follow-up of individuals following the occurrence of adverse events.

The investigator is responsible for appropriate medical follow-up of patients until resolution or stabilization of the effect or until the patient's death. This may sometimes mean that this follow-up extends beyond the patient's discharge from the trial.

He/she transmits the additional information to the sponsor using an SAE reporting form (checking the Follow-up No. X box to specify that it is a follow-up report and not an initial report) within 24 hours of obtaining it. It also forwards the last follow-up to the resolution or stabilization of the SAE.

He keeps the documents concerning the suspected adverse reaction in order to allow, if necessary, to complete the information previously transmitted.

It responds to requests for additional information to document the initial observation.

XII. STATISTICAL ANALYSIS

XII.1 Provisional timetable for the study

With an expected rate of one patient per month per center, i.e. 10 patients per month, and with a suspension of inclusions between stage 1 and 2, the study schedule will be as follows:

Stage 1: 43 evaluable patients

- Expected start date of inclusion (stage 1): September 2014
- Anticipated end date of inclusion stage 1: February 2015
- Judging criterion at 6 months: August 2015
- Stage 1 analysis (+ 6 months): February 2016

Stage 2: 43 evaluable patients

- Expected start date of inclusion: February 2016
- Expected completion date of inclusion stage 2: July 2016
- Judging criterion at 6 months: January 2017
- Final analysis of primary endpoint (+ 6 months): July 2017
- 2-year overall survival analysis: January 2020

XII.2 Judging criteria

XII.2.1 Main criterion

The primary endpoint is the rate of patients with objective response (complete response or partial response) **at 6 months after inclusion** according to mRECIST criteria and centralized review.

XII.2.2 Secondary Criteria

The secondary endpoints of this study are:

- The rate of patients in objective response** (complete response or partial response) at 6 months according to mRECIST criteria and evaluated by the investigator.
- The rate of patients in objective response** (complete response or partial response) at 6 months according to EASL criteria assessed by the investigator and in centralized review.

- Time to treatment failure

It is defined as the time interval between the date of inclusion and the date of protocol treatment failure. Death, progression, and any discontinuation of protocol treatment (regardless of cause) are considered treatment failures.

Patients alive without failure will be censored at the date of the last 6-month morphological evaluation.

- The best response according to the mRECIST criteria

- Progression-free survival

It is defined as the time interval between the date of inclusion and the date of 1st progression according to mRECIST criteria (assessed in centralized review) or death (regardless of cause).

Patients living without progression will be censored at the date of last news.

- Overall survival

It is defined as the time interval between the date of inclusion and the date of death (regardless of cause) or the date of last news for living patients.

- Tolerance of the treatment

Toxicities will be evaluated by the NCI-CTC v4.0 criteria. They will be described according to their grade in terms of number of toxicities and number of patients who experienced the toxicity.

- Quality of life (QLQ-C30 questionnaires and its HCC18 module specific to HCC)

XII.3 Calculation of the number of subjects needed

The assumptions are:

- H0: A proportion of patients with an objective response at 6 months of 25% or less is not acceptable
- H1: A proportion of patients with an objective response at 6 months of more than 25% would demonstrate the effectiveness of the treatment. A rate of 40% is hoped for.

Using a 2-stage Fleming design (Fleming, 1982) with a one-sided alpha risk of 5% and power of 90%, it is necessary to include **86 treated and evaluable patients**.

At the 1^{ère} stage: 43 patients will be included

- If 10 or fewer patients have an objective response, the trial will be stopped for futility (H1 rejection)
- If 18 or more patients have an objective response, the trial will be stopped for efficacy (rejection of H0)

If not, we will go to 2^{ème} step including 43 additional patients

If 29 or more patients have an objective response, the treatment is declared effective (rejection of H0)

Taking into account a 5% rate of patients lost to follow-up or not evaluable, **91 patients** will be included. The decision rules will be adapted based on the number of evaluable patients actually included.

XII.4 Statistical analysis plan

A statistical analysis plan will be written prior to freezing the database.

Analysis Populations:

The characteristics of the patients included in the study will be described in strict intention-to-treat (ITT). Efficacy analyses will be performed on a modified intention-to-treat (mITT) basis: all evaluable patients included in the study regardless of eligibility criteria. A patient is considered evaluable if he/she has had at least one chemoembolization and one post-treatment evaluation.

Population evaluable for safety:

The ITT population that received at least one chemoembolization.

Statistical analysis:

The description of the variables will be done using percentages (95% confidence interval) for qualitative variables and using mean (standard deviation) and median (Min-Max) as well as the inter-quartile range (Q1-Q3) for quantitative variables.

The estimation of censored data will be done by the Kaplan Meier (KM) method. Times will be described by medians and rates at different time points with their 95% confidence intervals. The median follow-up time will be calculated using the reverse Kaplan Meir method.

XII.5 Independent Committee

An independent committee composed of 1 clinician / 1 methodologist-statistician / 1 pharmacovigilant expert / 1 radiologist will be set up before the beginning of the trial. It will meet regularly during the course of the study according to the rate of inclusion.

It will have to rule on the declared ADRs. It can also be seized at any time by the Sponsor in case of significant facts on the tolerance (ADRs and AEs) of the treatment.

XIII. JUSTIFICATION OF THE TEST

A systematic review published by Marelli et al. showed that the most commonly used products in HEC were doxorubicin (36%), cisplatin (31%) and epirubicin (12%) [Marelli et al., CVIR 2007]. However, until recently, there was no clear rationale for choosing one molecule over another. Indeed, systemic chemotherapy is considered ineffective in HCC [Burrough, Lancet Oncol 2004], which does not provide an argument for the choice of the molecule. Moreover, 2 randomized trials that were designed to compare agents (doxorubicin versus epirubicin) were negative in terms of survival [Kawai, Sem Oncol 1997; Watanabe, Cancer Chemother Pharm 1994].

Very recently, a study conducted at the University Hospital of Dijon, compared the cytotoxicity of various anticancer agents on HCC cell lines, with the aim of selecting the best candidate for HEC (Boulin et al., Anticancer drugs 2011).

Eleven chemotherapy agents were tested, including those most commonly used for HEC. Idarubicin (an anthracycline) was by far the most effective in vitro. The superiority of idarubicin (over doxorubicin) was observed particularly in the SNU-449 line, which is known to be resistant to several chemotherapy agents [Park, JNCI 1994]. The better cytotoxicity of idarubicin can be explained by 2 mechanisms: 1) idarubicin has a better intracellular penetration than other anthracyclines [Broggini, Cancer Treat Rep 1984]. This is probably due to its greater lipophilicity, thus facilitating its passage through the membrane composed of a double lipid layer, 2) idarubicin has the property of resisting the multidrug resistance (MDR) system [Roovers, Leuk Res 1999]. The MDR mechanism, often observed in HCC, consists of membrane pumps that transport the molecule out of the cell. These two properties could explain a higher accumulation of idarubicin in HCC cells and thus a better efficacy. Interestingly, idarubicin administered orally (5mg/day for 21 days) has been shown to have low toxicity and efficacy in HCC [Tumolo, ASCO 2002]. Currently, idarubicin is used to treat leukemia. Its safety profile (in particular hematological and cardiac) is known.

Based on these findings, a pilot study was conducted to evaluate the safety and efficacy of lipiodol-based HEC using a dose of 10 mg idarubicin in 21 patients with unresectable HCC. These preliminary data show that HEC with idarubicin is effective and has low toxicity (Favelier et al., CVIR 2013).

As idarubicin can be loaded on microbeads, a phase I study (IDASPERE) (article submitted to Clin Cancer Research) with DC Bead® (300-500 μ m) loaded with idarubicin (dose escalation from 5 to 25 mg) was conducted at the Dijon University Hospital. DLT and MTD were determined in 21 patients using a CRM (Continual Reassessment Method). The MTD of idarubicin was evaluated at 10 mg. In this study, idarubicin-loaded beads did not pose any specific toxicity concerns.

The 10-mg dose is consistent with the well-known toxicity profile of idarubicin: cumulative cardiotoxicity of doxorubicin is observed from 550 mg/m², whereas that of idarubicin is observed from 93 mg/m². Thus, there is a 5.9:1 ratio between their cumulative toxicities. The most commonly used (and also the lowest) dose for doxorubicin-based HEC is 50 mg. The dose equivalent of idarubicin would therefore be: 50 mg (doxorubicin) / 5.9 (doxorubicin/idarubicin ratio) = approximately 10 mg of idarubicin.

It has already been shown that the hepatic extraction of idarubicin is better than that of doxorubicin and daunorubicin in an animal model of sarcoma. In this study, the AUC 0-48h and AUC 0-72h) were 1.35 times higher with idarubicin, showing that the intrahepatic penetration of the molecule was 35% higher [Broggini M et al. Cancer Treat Rep 1984].

The PRECISION V randomized phase II trial compared conventional HEC (cCHE) with doxorubicin-loaded bead HEC (DC Bead®) in patients with HCC (Lammer et al. CardioVasc Intervent Radiol. 2010). This is the largest published study of HEC. The PRECISION V data can therefore be used for comparison with other studies in terms of efficacy and safety.

As a follow-up to the preliminary study and the IDASPERE Phase I study, we would like to evaluate the efficacy and confirm the safety of idarubicin-loaded beads for HEC in a protocol similar to PRECISION V, in a single-arm Phase II setting.

XIV. REFERENCES

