Non-inclusion criteria	
 - Advanced tumor disease (vascular or extrahepatic invasion including brain metastases or diffuse HCC with $>$ 50% liver invasion) - History of other cancers excluding cancers known to be cured for more than 3 years (in this case histological evidence of HCC is required), or basal cell skin tumors or cervical cancer in situ adequately treated with curative intent - Previous treatment with idarubicin and/or doxorubicin - Contraindication to idarubicin (heart disease with myocardial insufficiency, severe renal or hepatic insufficiency, yellow fever vaccine) - Concomitant disease or severe uncontrolled clinical situation - Patients requiring long-term anticoagulant therapy - Thrombosis of the portal trunk or of a territory of 3 or more segments (or hepatofugal flow of the same territories) - Vascular involvement: 
 o severe atheromatous disease or, o collateral vascular pathways potentially endangering normal territories during embolization or, o arteritis of the branches of the hepatic artery to be treated or, o arterio-port or arterio-sus-hepatic fistula not embolisable by coils - Pregnancy or breastfeeding - Lack of effective contraception (for men or women of childbearing age) - Patient who for psychological, social, family or geographical reasons could not be followed regularly - Concurrent participation of the patient in another experiment
Study design and treatment plan	1 to 4 chemoembolisations (CHE) with idarubicin-loaded microbeads (100-300 μ m) (10 mg - Zavedos® Pfizer)

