Statistical methods	
The assumptions are:
 
 • H0: a proportion of patients with an objective response at 6 months of 25% or less is not acceptable • H1: A proportion of patients with an objective response at 6 months of more than 25% would show the effectiveness of the treatment. A rate of 40% is hoped for. 
Using a 2-stage Fleming design (Fleming, 1982) with a one-sided alpha risk of 5% and power of 90%, it is necessary to include 86 treated and evaluable patients.
 
At the 1^{ère} stage: 43 patients will be included
 
 - If 10 or fewer patients have an objective response, the trial will be stopped for futility (H1 rejection) - If 18 or more patients have an objective response, the trial will be stopped for efficacy (rejection of H0) 
If not, we will go to 2^{ème} step and include 43 additional patients.
 
If 29 or more patients have an objective response, the treatment will be declared effective (rejection of H0)
 
Taking into account a rate of 5% of lost to follow-up or not assessable, 91 patients will be included. The decision rules will be adapted based on the number of evaluable patients actually included.

Biological studies	Analysis of VEGF level by ELISA technique and progastrin level then correlation with tumor and non-tumor liver volumes.
Number of subjects needed	91
Planned study period	
Rate of 10 patients per month (1 patient per month per center - 10 centers)
 
Expected start date of inclusions: September 2014.
 
Expected completion date of inclusions (stage 2): July 2016
 
Expected completion of study: January 2020

EXAMINATION AND FOLLOW-UP SCHEDULE

	BEFORE TREATMENT	DURING TREATMENT with CHE			AFTER 6 MONTHS (patient follow-up)	
	Within 28 days before 1 ^{ière} HEC and before inclusion	Before each HEC	After each HEC	At 6 months after inclusion	1 ^{ière} year every 3 months	2 ^{ième} year every 6 months
Clinical and biological informed consent	X					
CLINICAL EXAMINATION						
Weight, height, pain assessment (VAS)	X	X			X	
General status WHO	X	X			X	
Child-Pugh if associated cirrhosis and BCLC score	X					
Quality of life (QLQ-C30 and HCC-18)	X	X				
Description of the disease and medical history	X	X				
Toxicity assessment (NCI-CTC v4.0)			X	X		
MORPHOLOGICAL EXAMINATIONS*** (IN FRENCH ONLY)						
Hepatic MRI	X		X	X	X****	X****
Ultrasound of the liver					X****	X****

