CAT scan for extra-hepatic evaluation	X		X (in case of contraindication to MRI)	X	X (thoracic every 6 months)	X (thoracic)
Portal Doppler if thrombosis is suspected on imaging	X	X (recommended)				
ECG	X					
Evaluation of left FEV	X					
BIOLOGICAL ASSESSMENT						
Biological check-up	X*	X**			X (liver test)	X (liver test)
AFP marker	X				X	X
Serology (HBsAg, anti-HBs, anti-HCV)	X					
Pregnancy test (within 7 days of inclusion)	X					
BIOLOGICAL STUDY						
Samples: 2 EDTA tubes of blood then centrifugation for aliquoting of 4 cryotubes of plasma and freezing at -20°C then -80°C		X (D0, D1, D2 and D3 of 1 ^{ière} HEC)				
IMAGERY*** : CT cone beam or CT scan without injection during the procedure						

* Complete biological check-up: CBC/platelets, PT, AST, ALT, alkaline phosphatases, GGT, bilirubin (total, free and conjugated), factor V, blood ionogram, creatinine, albumin, blood sugar, blood calcium

** Biological check-up before each HEC: CBC, platelets, blood ionogram, creatinine, albumin, ASAT, ALAT, PAL, GGT, total and conjugated bilirubin, PT

*** : An anonymized copy of the imaging is to be sent to the FFCD for centralized review

**** : hepatic MRI (or CT) / ultrasound of the liver by a trained operator alternating every 3 months for 2 years

I. OBJECTIVES OF THE TRIAL

I.1 Main objective

The objective of this non-randomized phase II study is to evaluate the objective response rate (complete and partial response) at 6 months, assessed according to the mRECIST criteria in centralized review.

I.2 Secondary objectives

The secondary objectives of this study are to evaluate:

- The investigator-assessed 6-month objective response rate (mRECIST)
- Time to treatment failure
- The best answer according to mRECIST
- Objective response rate at 6 months (EASL)
- Progression-free survival
- Overall survival
- Tolerance of the treatment
- Quality of life (QLQ-C30 questionnaires and its HCC18 module specific to HCC)

II. PATIENT SELECTION

II.1 Inclusion criteria

- Histologically proven HCC or according to EASL/Barcelona criteria for nodules ≥ 1 cm
- Tumor not amenable to curative treatment (liver transplantation, surgical resection or percutaneous destruction)
- Measurable targets according to mRECIST v1.1 criteria
- Preserved liver function (in case of cirrhosis, Child-Pugh A or B7 without history of edemato-ascitic decompensation)
- Tumor classified as BCLC A or B without portal or extrahepatic invasion or C if WHO= 1

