- No prior treatment with chemotherapy, radiotherapy or transarterial embolization (with or without chemotherapy)
- Age ≥ 18 years
- WHO 0 or 1
- Biological workup: platelets $\geq 50,000/\text{mm}^3$, PNN $\geq 1,000/\text{mm}^3$, creatinine level $\leq 150 \mu\text{mol/L}$
- No heart failure (isotopic or echographic LVEF $> 50\%$)
- Signed informed consent

II.2 Non-inclusion criteria

- Advanced tumor disease (vascular or extrahepatic invasion including brain metastases or diffuse HCC with $> 50\%$ liver invasion)
- History of other cancers excluding cancers known to be cured for more than 3 years (in this case histological evidence of HCC is required), or basal cell skin tumors or cervical cancer in situ adequately treated with curative intent
- Previous treatment with idarubicin and/or doxorubicin
- Contraindication to idarubicin (heart disease with myocardial insufficiency, severe renal or hepatic insufficiency, yellow fever vaccine)
- Concomitant disease or severe uncontrolled clinical situation
- Patients requiring long-term anticoagulant therapy
- Thrombosis of the portal trunk or of a territory of 3 or more segments (or hepatofugal flow of the same territories)
- Vascular involvement:

- severe atheromatous disease or,
- collateral vascular pathways potentially endangering normal territories during embolization or,
- arteritis of the hepatic artery branches to be treated, or
- arterio-port or arterio-sus-hepatic fistula not embolisable by coils
- Pregnancy or breastfeeding
- Lack of effective contraception (for men or women of childbearing age)
- Patient who for psychological, social, family or geographical reasons could not be followed regularly
- Concurrent participation of the patient in another experiment

III. PRE-INCLUSION ASSESSMENT

To be performed within 28 days prior to treatment and before inclusion:

Full clinical examination:

- Weight, height, vital signs, WHO index, pain assessment (VAS)
- Child-Pugh score if associated cirrhosis, BCLC (Barcelona Clinic Liver Cancer) score (Appendix 4)
- Medical history
- Description of the disease
- Quality of life (QLQ-C30 and its module HCC18)

Complete biological workup:

- CBC, platelets, PT, AST, ALT, PAL, GGT, bilirubin (total, free and conjugated), factor V, blood ionogram, creatinine, albumin, blood glucose, blood calcium
- Markers: α -fetoprotein (AFP)
- Serology: HBsAg, anti-HBc, anti-HCV,

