- Digestive disorders: nausea, vomiting, diarrhea
- Stomatitis, esophagitis
- Elevated liver enzymes and bilirubin in 20-30% of cases
- Skin rash
- Acute heart rhythm disturbances, acute or late heart failure (rare before a cumulative dose of 93 mg/m²)
- Red coloration of the urine 24 to 48 hours after treatment.

As with other DNA altering anticancer agents, myelodysplastic syndromes and acute myeloid leukemias have been observed after combination therapy with anthracycline.

In case of idarubicin-related effects, no dose adjustment of idarubicin for loading the microbeads is planned. The chemoembolization session is then postponed or cancelled.

VII. MONITORING DURING AND AFTER TREATMENT

VII.1 Before each HEC

- Complete clinical examination: weight, vital signs, WHO general condition (which should be 0 or 1), pain assessment (VAS)
- Biological work-up: CBC/platelets, blood ionogram, creatinine, albumin, transaminases (AST, ALT), alkaline phosphatases (ALP), GGT, total and conjugated bilirubin, PT
- Adverse event evaluations of previous HECs according to NCI CTC version 4.0
- Quality of life questionnaires (QLQ-C30 and its module HCC18)

Prior to the session, the investigator should ensure that the patient has adequate hepatic and hematological function:

- Bilirubin ≤ 1.5 mg/dL, PNN $\geq 1,000/\text{mm}^3$, platelets $\geq 50,000/\text{mm}^3$, creatinine level $\leq 150 \mu\text{mol/L}$
- Hepatopoietic flow, thrombosis is considered significant if it involves at least 3 segments. The procedure is then contraindicated. A Doppler is strongly recommended before the embolization sessions to ensure that the procedure can be performed. It is recommended to evaluate these criteria according to the habits of the center.

For patients participating in the translational study: blood sampling for translational study (see paragraph IX)

VII.2 After each HEC

Hepatic MRI (or CT scan in case of contraindication to MRI) will be performed 4 to 6 weeks after each chemoembolization to assess their effectiveness.

Assessment imaging at 6 months from the date of inclusion MUST be performed regardless of the time of last HEC to assess the primary endpoint of the study.

Target measurements will be done according to mRECIST v1.1 to assess the primary endpoint of the study and according to EASL criteria to assess the secondary endpoint (Appendices 4 and 5).

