An anonymized copy on CD ROM (present in each observation book) of each morphological evaluation until progression (even if beyond 6 months) (MRI) is to be made. The copies will be sent to the CRGA of the FFCD for centralized review .

For the translational study, perform a cone beam CT acquisition or a hepatic CT scan without injection at the time of the 1^{ère} HEC.

For the clinical study, if possible, perform a cone beam CT acquisition at each HEC to assess the quality of the chemoembolization.

VII.3 Post-treatment monitoring beyond 6 months after inclusion:

After the end of chemoembolization treatment, patients will be followed according to TNCD recommendations:

Clinical and biological evaluation every 3 months for the first year and then every 6 months for 1 year:

- Clinical examination (weight, WHO)
- Biological tests: liver tests (ASAT, ALAT, GGT, bilirubinemia, albuminemia, TP)
- Marker : AFP

Morphological assessment:

- Chest CT scan without injection, every 6 months for 2 years
- Hepatic MRI (or CT scan) - liver ultrasound by a trained operator alternating every 3 months for 2 years

Monitoring data will be collected in the observation book during this 2-year period.

VIII. STOP PROCESSING THE STUDY

The processing of the study will be stopped in case of:

- Investigator's decision
- Major toxicity requiring discontinuation of treatment
- Serious or unexpected event requiring discontinuation of protocol treatment
- Progression of the disease
- Patient refusal or withdrawal of consent
- Death of the patient

In all cases of treatment discontinuation, the patient remains in the analysis for intention-to-treat and overall survival, and for 30 days after the last study treatment for toxicity.

There is no exclusion period for a subsequent therapeutic trial.

IX. TRANSLATIONAL STUDY

Only patients who have signed their translational-biological informed consent will be collected. Rationale for the study (see Appendix 15).

Blood sampling for VEGF determination

- 4 sampling times:

After the 1^{ière} HEC at D0, D1, D2 and D3

- Samples :

At each sampling time (4 times), collect 2 x 7 ml EDTA tubes of blood.

Centrifuge the blood tubes at room temperature at 1000 g for 15 minutes.

Collect the plasma to be distributed in a minimum of 4 cryotubes (minimum 1 mL per cryotube).

Identify the cryotubes with the patient's initials + inclusion number in the study, the sampling times.

Freeze the 2 plasma cryotubes at -20°C then at -80°C.

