## **7.6 Quality of life assessment**

Quality of life is assessed using the EORTC QLQ-C30 and HCC18 questionnaires.

The scores of these questionnaires at inclusion will be described using standard statistics.

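### Quality of life is a secondary objective, but no questionnaire is scheduled after the last session or at 6 months, and the SAP analyses only the scores at inclusion

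*Protocol*

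**What the plan says.** **Objective.** Protocol I.2 and XII.2.2 list "Quality of life (QLQ-C30 questionnaires and its HCC18 module specific to HCC") among the secondary items, and SAP 3.1.2 repeats it. No time point, scale of interest or summary measure is attached.

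**Collection.** In the protocol's examination and follow-up schedule, the row "Quality of life (QLQ-C30 and HCC-18") is marked before treatment and before each session (HEC in the documents). It is blank after each session, at 6 months and in both follow-up years. The body text matches:

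- Section III, pre-inclusion assessment: "Quality of life (QLQ-C30 and its module HCC18").
- Section VII.1, before each session: "Quality of life questionnaires (QLQ-C30 and its module HCC18").
- Section VII.2, after each session and at 6 months: "Assessment imaging at 6 months from the date of inclusion MUST be performed regardless of the time of last HEC". No questionnaire is listed.
- Section VII.3, beyond 6 months: "Clinical examination (weight, WHO"), liver tests, AFP and imaging. No questionnaire is listed.

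**Analysis.** SAP 7.6 names the two instruments and then plans one thing: "The scores of these questionnaires at inclusion will be described using standard statistics". The SAP plans no other quality-of-life analysis.

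**Number of sessions.** The synopsis allows "1 to 4 chemoembolisations (CHE) with idarubicin-loaded microbeads", so a single session is a complete course.

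**The concern.** There are two gaps. The first is in collection: because each questionnaire during treatment is tied to an upcoming session, the last one always precedes the last treatment. The effect of that session is never measured on schedule, and patients who stop after one session contribute only pre-treatment values. The second is in analysis: even the questionnaires that are collected before sessions 2 to 4 have no planned use.

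At stake is whether the trial can say anything about quality of life under this treatment. With baseline scores alone, the report would describe the patients at entry and leave the objective unanswered. If the later scores were used without comment, they would describe patients who were due for another session, not the trial population.

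**Working it through.** The documents give no quality-of-life figure to reproduce. The check is of timing and of who supplies later values.

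**Inputs.** First session within 0 to 2 weeks of inclusion (protocol IV); interval 6 weeks plus or minus 1, so 5 to 7 (protocol VI.1); 1 to 4 sessions (synopsis); 1 month = 30.4375 days (SAP 6.2).

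**Six months in weeks.** 6 × 30.4375 / 7 = 182.625 / 7 = 26.1.

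**Week of the last scheduled questionnaire** with k sessions, first-session delay d and interval i: d + (k-1) × i.

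| Sessions k | Earliest (d=0, i=5) | Latest (d=2, i=7) | Weeks short of 6 months | Scheduled values after a first treatment (k-1) |
|---|---|---|---|---|
| 1 | 0 | 2 | 24.1 to 26.1 | 0 |
| 2 | 5 | 9 | 17.1 to 21.1 | 1 |
| 3 | 10 | 16 | 10.1 to 16.1 | 2 |
| 4 | 15 | 23 | 3.1 to 11.1 | 3 |

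Even with four sessions at the slowest planned pace, the last questionnaire comes 3.1 weeks before the 6-month point, and it still precedes the fourth session. SAP 7.6 uses none of the k-1 later values.

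**Who supplies later values** (protocol V.2.3 and VII.1):

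- patients with bilobar disease, for whom two sessions are planned from the start;
- patients with a remnant or recurrence that can be treated again, who still have WHO status 0 or 1 and acceptable liver function, blood counts and portal flow.

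**Who stops supplying them** (protocol VI.1):

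- complete responders;
- patients whose previously treated tumor progresses;
- patients with grade 3 or 4 non-hematological toxicity attributed to the session. The next sentence of VI.1 leaves some toxicity cases to the investigator's discretion, so this group's boundary is not sharp.

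The first group to stop has done well and the other two badly. The sign of the resulting bias cannot be derived from the documents.

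**Number of single-session patients.** The documents do not give it. As an assumption only, 20% to 50% of the 46 patients in SAP 4.6.1 would be 0.20 × 46 = 9.2 to 0.50 × 46 = 23, so about 9 to 23 without a scheduled post-treatment value. The conclusion does not depend on this range.

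**The case against.** The strongest reply is that the objective says only quality of life. It promises neither a 6-month value nor a change score, and it is descriptive, in a single-arm trial, with no bearing on the primary decision. Questionnaires before sessions 2 to 4 fall 5 to 7 weeks after the previous session and are real on-treatment data. That stands. A reader might infer that the objective is wholly unanswerable; the documents do not support this, because patients with two or more sessions do give post-treatment values. What cannot be estimated is quality of life in the whole trial population, after the last session, or at 6 months.

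Three other inferences also go too far:

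- That no patient can have a value near 6 months. None is scheduled, but V.2.3 allows retreatment after 3-monthly surveillance, and VI.1 allows longer intervals with the coordinator's agreement. A pre-session questionnaire could fall there by chance, in selected patients.
- That later values come only from patients retreated for remnant or recurrence. Bilobar patients have a second session planned upfront.
- That the missing patients are those with the best outcomes. Progression and toxicity also end measurement.

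A last objection is that changing the schedule now achieves little. SAP 4.6.1 reports the trial stopped for efficacy at the January 2017 interim analysis, with 46 patients included and 44 already evaluable for the 6-month endpoint. That also stands, and it moves the remedy to the SAP.

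**Conclusion.** The point holds. The schedule and body text agree, so this is not an extraction artefact: questionnaires are scheduled only at baseline and before each session. Because SAP 7.6 describes only scores at inclusion, the plan as written reports the secondary objective with baseline data alone. Single-session patients have no scheduled post-treatment value, patients with k sessions have k-1, and no questionnaire is scheduled after the last session or at 6 months. The week ranges assume the planned 5-to-7-week interval and a start within 2 weeks. The k-1 count and the absence of any scheduled value after the last session do not need that assumption.

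The later values form a selected set with a bias of unknown direction. The primary endpoint is unaffected. The analysis gap is the part that can still be closed, since SAP 4.6.2 treats the final analysis as yet to be done.

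**What to change.** **In SAP 7.6:**

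- Describe QLQ-C30 and HCC18 scores, and change from baseline, at each pre-session questionnaire, using the baseline definition already in SAP 6.5.
- At each one, give the number of questionnaires expected (patients reaching that session) and completed.
- State who contributes later values and who does not, and that the direction of bias is unknown.
- Limit the quality-of-life conclusion to the period before the last session.

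**In the protocol schedule and VII.2:** add the questionnaire at the mandatory 6-month visit only for patients not yet past it, if any. On the SAP 4.6.1 figures, at most 46 - 44 = 2 of the 46 were not evaluable for that endpoint, and the documents do not say whether either still had the visit ahead. This addition cannot replace the SAP change.

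**Cost:** a few more descriptive tables from data already collected, and a narrower quality-of-life conclusion. More tables will not remove the selection, so the limitation has to be stated alongside them.
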